2.0 OBJECTIVE(S) & HYPOTHESIS (ES)

Primary Objective:

1. To determine the disease free survival (DFS) at 2 years of patients with maintenance therapy using pembrolizumab in combination with standard adjuvant hormonal therapy.

Hypothesis: Pembrolizumab maintains the disease-free status of patients with HR-positive primary IBC who have less than pathological complete response from neoadjuvant chemotherapy.

2. To determine the safety and toxicity profile of primary IBC patients who received combination of pembrolizumab and hormone receptor blockade.

Exploratory Objective

To investigate the association between immune related biomarkers in the peripheral blood and tumor tissue, such as PD-L1 expression, with safety and efficacy for IBC patients treated with pembrolizumab.

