4.6 Criteria for Disease Control

The purpose of this study is to maintain progression free status by additional immune modulation with pembrolizumab to enhance the surveillance and suppression of tumor that is currently done only by hormone receptor blocking agents.

4.6.1. Response will not be considered evaluable in the following categories:

4.6.1.1. Early Deaths: Patients who die within the first 2 weeks of the initiation of drug therapy owing to concurrent disease. These cases will be considered treatment failures in the intent-to-treat analysis.

4.6.1.2. Lost to Follow-up: Patients for whom there is inadequate information to judge tumor response because of loss of contact with our institution (>2 months after a missed appointment) and with referring physician in spite of repeated attempts to locate them. These cases will be considered treatment failures in the intent-to-treat analysis.

4.6.1.3. Major Protocol Violation: Patients who significantly deviate from the treatment program by either adding or deleting another agent or another therapeutic maneuver or by modifying schedule substantially (delay treatment ≥ 7 days without administration reason) of the drug under evaluation. Patients who do not fulfill the requirements outlined under Patient Eligibility are also included in this category. Patients on the concurrent radiation arm due to excess toxicity who do not complete the planned radiation will not be considered violations if they continue systemic therapy per protocol plan

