7.0 SAFETY MONITORING AND REPORTING

7.1 Assessing and Reporting Adverse Event

An adverse event is defined as any untoward medical occurrence in a patient or clinical investigation subject administered a pharmaceutical product and which does not necessarily have to have a causal relationship with this treatment. An adverse event can therefore be any unfavorable and unintended sign (including an abnormal laboratory finding, for example), symptom, or disease temporally associated with the use of a medicinal product or protocol-specified procedure, whether or not considered related to the medicinal product or protocol-specified procedure. Any worsening (i.e., any clinically significant adverse change in frequency and/or intensity) of a preexisting condition that is temporally associated with the use of the pembrolizumab, is also an adverse event.

Adverse events may occur during the course of the use of pembrolizumab in clinical trials, or as prescribed in clinical practice, from overdose (whether accidental or intentional), from abuse and from withdrawal.

Progression of the cancer under study is not considered an adverse event.

All adverse events that occur after the consent form is signed but before treatment allocation/randomization must be reported by the investigator if they cause the subject to be excluded from the trial, or are the result of a protocol-specified intervention, including but not limited to washout or discontinuation of usual therapy, diet, placebo treatment or a procedure.

From the time of treatment allocation through 30 days following cessation of treatment, all adverse events must be reported by the investigator. Such events will be recorded at each examination on the Adverse Event case report forms/worksheets. The reporting timeframe for adverse events meeting any serious criteria is described in section [7.6](#). The investigator will make every attempt to follow all subjects with non-serious adverse events for outcome.

Adverse events will not be collected for subjects during the pre-screening period as long as that subject has not undergone any protocol-specified procedure or intervention.

Adverse events will be assessed according to the CTCAE version 4.0. All study patients who have received any dose of pembrolizumab will be evaluable for safety. Unexpected adverse events including laboratory adverse events deemed clinically significant by the investigator will be graded and recorded.

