0.50	24.0	0.775	19.0
0.60	18.2	0.947	13.7

Safety Run-in

At any time within first 6 patients are treated, if ≥ 2 patients experience serious adverse events (SAE) within first 3 cycles of treatment, we will stop the trial and claim that the regimen is too toxic. An SAE is defined as an adverse event that is serious, unexpected, and related to the study drug. This study will be monitored by the IND Office. During the safety run-in and throughout the study, patients who have completed 3 cycles of treatment will be considered as evaluable for safety and response.

Analysis of Primary and Secondary Endpoints

The primary endpoint of DFS will be summarized at 2 years with a corresponding 95% confidence interval. DFS will be compared with the historical control rate of 60% at year two by using a one-sided exponential MLE test. Cox proportional hazards regression analysis will be used to model the association between DFS and disease and demographic covariates of interest, including immune-related biomarkers in the peripheral blood and tumor tissue. Overall survival (OS) from the start of the study will be analyzed similarly to DFS. Adverse events will be summarized by grade and category.

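### Section 8 ties evaluability for safety to completing 3 cycles, Section 7.1 asks only for any dose of pembrolizumab, and nothing reconciles the two

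*Combined protocol and SAP*

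**What the plan says.** Two places define who is evaluable for safety.

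- Section 8.0, Safety Run-in: "patients who have completed 3 cycles of treatment will be considered as evaluable for safety and response". The same sentence applies this to the run-in and to the whole study.
- Section 7.1: "All study patients who have received any dose of pembrolizumab will be evaluable for safety".

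Four other texts bear on the choice.

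- Section 2.0 lists safety under the primary objectives: "To determine the safety and toxicity profile of primary IBC patients who received combination of pembrolizumab and hormone receptor blockade".
- The AE analysis in Section 8.0 names no analysis set: "Adverse events will be summarized by grade and category".
- The run-in trigger opens with "At any time within first 6 patients are treated" and counts patients who "experience serious adverse events (SAE) within first 3 cycles of treatment"; two or more such patients stop the trial.
- Section 4.6.1 opens a list with "Response will not be considered evaluable in the following categories". For early deaths and for losses to follow-up it adds: "These cases will be considered treatment failures in the intent-to-treat analysis". Section 8.0 does not take up this intent-to-treat analysis, and it names no set for DFS.

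**The concern.** The two definitions give different denominators for the same tables. If one dose is enough, completing 3 cycles adds nothing to a patient's standing for safety. The Section 8 sentence therefore most naturally works as a restriction, particularly as it is not confined to the run-in. A cycle is 3 weeks (Section 4.2.1.1), so the condition takes about 9 weeks to meet. The dose modification table in Section 4.2.2 ends treatment permanently for several toxicities, so a 3-cycle condition can remove patients because of the events that the safety objective is meant to describe. That bias is in the favourable direction.

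The term is already in use. Section 4.2 reports an interim safety table on 3 evaluable patients without saying which definition applied, and cites it in reducing the frequency of physician follow-up. This does not show that anyone was left out. It shows that the undefined term already carries safety conclusions.

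**Working it through.** **Texts side by side**

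| Place | Who counts for safety |
|---|---|
| Section 2.0, objective 2 | Patients who received the combination |
| Section 7.1 | Anyone given any dose |
| Section 8.0, run-in trigger | The first 6 treated patients |
| Section 8.0, evaluability sentence | Patients who completed 3 cycles |
| Section 8.0, AE summary | Not stated |

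One text departs from the other three that name a group. A patient among the first 6 who has a qualifying event and stops before finishing cycle 3 counts under the trigger, but falls outside the evaluability sentence in the same paragraph.

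**Size of the bias if the sentence restricts**

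The documents give no AE rates by cycle and no early-exit rates, so there is no stated figure to reproduce and the inputs below are assumptions. Let p be the true share of treated patients with the AE, f the share of affected patients who do not complete 3 cycles, and g the same share among unaffected patients. The rate among completers is

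p(1 − f) / [p(1 − f) + (1 − p)(1 − g)],

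which reduces to p(1 − f) / (1 − pf) when g = 0.

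With p = 0.20 and g = 0:

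- f = 0.05: 0.190 / 0.990 = 0.192
- f = 0.15: 0.170 / 0.970 = 0.175
- f = 0.50: 0.100 / 0.900 = 0.111

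In 37 treated patients, 0.20 × 37 = 7.4 are affected. The expected number dropped is 7.4 × 0.05 = 0.4, 7.4 × 0.15 = 1.1, or 7.4 × 0.50 = 3.7.

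With f = g = 0.10, the result is 0.18 / (0.18 + 0.72) = 0.20. There is no bias when unaffected patients leave as often as affected ones.

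**Which f is reasonable**

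Treatment runs for up to 24 months, or 34 cycles (Sections 4.2 and 5.0). Many AEs will start after cycle 3, in patients who have already met the condition and stay in the count. Section 4.2.2 holds and restarts treatment for many Grade 2 and some Grade 3 events. For overall AE rates a small f is therefore the sensible illustration. The value 0.50 suits only early AEs that force discontinuation.

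**DFS set**

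The 3-cycle sentence speaks of response, and Section 8.0 analyses no response endpoint. Section 8.0 caps the number treated at 37, and Section 4.6.1 uses intent-to-treat wording. Both point to all treated patients. The stated confidence interval width of about 25% reproduces on 37 patients, 2 × 1.96 × √(0.8 × 0.2 / 37) = 0.258. That calculation assumes no dropout, so it does not identify the intended set. One mismatch remains: Section 4.6.1.2 counts losses to follow-up as failures, whereas the monitoring rule in Section 8.0 allows right-censored times.

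**The case against.** The strongest reply is that the Section 8 sentence is not a restriction. It lacks the word only, and it closes a paragraph whose observation window is 3 cycles. It can be read as saying when a patient without an event counts as fully observed. Section 7.1, objective 2 and the AE summary sentence all lean towards any dose. This reading is possible, and it rules out saying that the plan announces a completer analysis. It does not remove the conflict: the sentence covers the whole study and names safety, and nothing ranks it below Section 7.1.

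A second reply is that the bias may be trivial. That largely stands. At small f the distortion is one or two percentage points, and it vanishes if unaffected patients leave equally often.

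Two stronger inferences are tempting, and the documents do not support them.

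- A reader might infer that the run-in rule would miss events in patients who stop early. The trigger is already worded on treated patients, so this is a risk of misreading and not a stated defect.
- A reader might infer that DFS, its monitoring rule and its test would be run on 3-cycle completers. The sentence says response, and the treated-patient cap and the intent-to-treat wording point the other way. No effect on the stopping probability, false-positive rate or DFS estimate is claimed. Agreement of a simulation without early exits with Table 5 would show only that exits were not simulated.

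**Conclusion.** The conflict over the safety set stands and should be fixed. Two sections give different denominators for an objective listed as primary, and the Section 8 rule, followed as a restriction, would remove early toxicity stoppers and understate AE rates.

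The size cannot be determined from the documents. At an assumed 5 to 15% of affected patients stopping before completing 3 cycles, with no early exits among the others, 20% reads 19.2 to 17.5%. The 11% figure, with half stopping, is an upper illustration for early AEs that force discontinuation and should not be quoted for AE rates in general.

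The unnamed DFS set is a secondary gap. The documents lean towards all treated patients without saying so.

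**What to change.** 1. In Section 8, delete the 3-cycle condition for safety. State that the safety set is all patients with at least one dose of pembrolizumab, as Section 7.1 already says, and attach that set to the AE summary.
2. Reconcile the evaluability sentence with the run-in trigger in the same paragraph, so that it cannot be read as removing a treated patient who has a qualifying event within the first 3 cycles and then stops. The trigger itself does not change.
3. State that the 3-cycle sentence does not define the DFS set, and name all treated patients for DFS.
4. Align this with Section 4.6.1. In particular, say whether a patient lost to follow-up is a failure, as that section has it, or is right-censored, as the monitoring rule allows.

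The cost is an amendment to wording. The sample size and monitoring thresholds stay as they are. Reported AE rates may be slightly less favourable than on a completer set.

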A fixed dose regimen will simplify the dosing regimen to be more convenient for physicians and to reduce potential for dosing errors. A fixed dosing scheme will also reduce complexity in the logistical chain at treatment facilities and reduce wastage.

Apart from the phase 1 study with Pembrolizumab and SBRT that is already published, there is published safety data from the phase 3 study PACIFIC in non-small-cell lung cancer with the PD-1 antibody Durvalumab¹⁶. The PACIFIC study included stage III NSCLC patients who had not progressed following definitive chemoradiation and showed both an increase in PFS by 11 months in the Durvalumab group as well as no significant difference in toxicity between groups. Of specific note, the incidence of grade 3/4 pneumonitis was 3.4% versus 2.6% in the placebo arm. This is encouraging given that the majority of patients in that study received definitive lung radiation to a dose of 54-66Gy. For patients with IBC, post-mastectomy radiation is a key part of trimodality treatment, and our typical target dose for the chest wall is in this range, hence lung dose would be considerably less, so we would not expect significantly higher rates of pneumonitis as a result of the concurrent radiation.

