4.2 Treatment Plan

The treatment to be used in this trial is outlined in Table 1 below.

Drug	Dose/Potency	Dose Frequency	Route of Administration	Regimen/ Treatment Period	Use
pembrolizumab	200 mg	Every 3 weeks	IV infusion	Up to 24 months or until meet drug discontinuation criteria (See 4.5)	Experimental

Drug	Dose/Potency	Dose Frequency	Route of Administration	Regimen/ Treatment Period	Use
The pembrolizumab dosing interval may be increased due to toxicity described in 4.2.2 .					

Based on our experience with very minimal side effects observed in the first 3 evaluable patients (see Table 2) as well as the design of another adjuvant Pembrolizumab study ongoing in triple negative breast cancer, physician follow-up will be reduced to every 2 cycles during the study due to the known side effect profile of Pembrolizumab.

Table 2: Interim safety analysis (3 evaluable patients, as of November 2017)

AE	Grade	Total # of patients
Fatigue	Grade 1	2
Nausea	Grade 1	1
Hot flashes	Grade 1	2
Headaches	Grade 1	1
Agitation	Grade 1	1
Skin itching	Grade 1	2
Vomiting	Grade 1	1
Dizziness	Grade 1	1
Eye disorders - eyelash thinning	Grade 1	1
Arthalgia	Grade 1	1
Rash	Grade 1	1

Based on emerging safety and efficacy data, as described in section 3.1.4, study treatment may be given concurrently with radiation based on physician and/or patient preference, but is not required. For patients consented prior to radiation who meet other eligibility criteria to allow concurrent radiation, pembrolizumab treatment will begin 7 days (± 3 days) after initiating radiation. During radiation, adverse events will be collected weekly, and patients will continue twice-weekly/weekly follow up visits with radiation oncologists as per standard procedure at MD Anderson for IBC patients receiving radiation. Special attention will be placed to minimize off-target dose to the lung, owing to the risk for pneumonitis in patients receiving immune checkpoint therapy.

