5.0 STUDY FLOW CHART

Trial Period:	Screening Phase	Treatment Cycles								End of Treatment ^h	Post-Treatment		
		1	2	3	4	8 cycles and beyond					If patient returns to clinic	Safety follow up ^f	Follow Up ^g
Treatment Cycle/Title:	Screening /Baseline												
Scheduling Window (Days):			± 3	± 3	± 3	± 3	± 3	± 3	± 3			1 month after last dose	24 months
Informed Consent	x												
Inclusion/Exclusion Criteria	x												
Demographics and Breast Cancer History ^a	x												
Concomitant Medication Review per SOC	x												
Physical Exam ^b , V/S	x	x	x	x	x	x	x	x	x	x			
Adverse Events ^b	x	x	x	x	x	x	x	x	x	x	x	x	
ECOG Performance Status ^b	x	x	x	x	x	x	x	x	x	x			
Pregnancy Test – Urine or Serum β-HCG (for women with childbearing potential)	x												
CBC and Biochemical Profiles ^c	x	x	x	x	x	x	x	x	x	x			
TSH, Free T4 and Total cortisol ⁱ	x			x		x		x		x			
Radiological Evaluation as clinically indicated and as SOC ^d	x									x			
Archived biopsy and/or surgical specimens (block or unstained slides) obtained at any time prior to treatment.	x												
Correlative Studies Blood Collection ^e	x				x			x		x			
Optional tumor sample collection at disease progression, if the site is accessible										x			
Disease Progression Status												x	
Pembrolizumab Administration		x	x	x	x	x	x	x	x				
Hormonal Therapy		x	x	x	x	x	x	x	x				
Radiation Therapy ^j		x	x										

- a. Demographics include patient's age, gender and race. Medical history includes primary breast cancer pathological diagnosis, ER/PR/HER2 status. Prior therapies and procedures for breast cancer,
- b. Complete physical exam, ECOG performance status and adverse events assessment during the screening period will not be repeated if done within 30 (+/- 3 days) days before the start of treatment. Physical exam will be performed every 2nd cycle throughout the study unless the patient is having side effects that require more frequent monitoring. Adverse events will be collected each cycle – on cycles when a physician follow-up is not scheduled, the study coordinator will meet with the patient to review these. For patients who are receiving concurrent radiation with study treatment, adverse events will be monitored on a weekly basis during the radiation therapy period.

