10.0 DATA MANAGEMENT

The Principal Investigator is responsible for assuring that the data entered into the database are complete and accurate and that data entry is performed in a timely manner.

10.1 Data collection for this study including:

- 1) demographic information (sex, race, and date of birth),
- 2) date of initial breast cancer diagnosis, pathology report of primary breast cancer, biomarker status, and date and location of distant metastases at disease progression;
- 3) history of breast cancer surgery, and radiation therapy, if applicable; radiation therapy timing with respect to initiation of pembrolizumab
- 4) date and type of chemotherapy and/or hormonal therapy for metastatic disease;
- 5) All AEs will be collected, however only $>/=2$ non-hematologic AEs and $>/=3$ hematological AEs will be recorded. Other abnormal laboratory values will not be reported as AEs; however, any clinical consequences of abnormality should be reported as AEs.
- 6) Concomitant medication will be recorded per standard of care in the electronic medical record, and will not be recorded in the study database.
- 7) All data collected for this study will be shared with Baylor College of Medicine ([name]) with compliance of data confidentiality plan.

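### The adverse-event summary is not split by concurrent radiation, so the pooled figures can hide the toxicity of the concurrent regimen

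*Combined protocol and SAP*

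**What the plan says.** Section 2.0 places safety second under the Primary Objective: "To determine the safety and toxicity profile of primary IBC patients who received combination of pembrolizumab and hormone receptor blockade". Radiation is not mentioned there.

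Section 4.2 makes radiation during treatment optional: "study treatment may be given concurrently with radiation based on physician and/or patient preference, but is not required". In patients who have it, pembrolizumab starts 7 days (± 3) after radiation begins. Footnote j of the Section 5.0 flow chart says the same.

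The review schedule differs while radiation is given. Section 4.2 states "During radiation, adverse events will be collected weekly", and flow chart footnote b states "adverse events will be monitored on a weekly basis during the radiation therapy period". Otherwise events are collected at each cycle, which Section 4.2.1.1 defines as 3 weeks. Section 7.1 adds a toxicity diary filled in daily, not limited to irradiated patients.

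The analysis in Section 8.0 is one sentence: "Adverse events will be summarized by grade and category". Section 10.1 item 3 lists "radiation therapy timing with respect to initiation of pembrolizumab" among the data collected, but no planned safety analysis uses it.

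**The concern.** The single summary covers two exposures. Patients irradiated before entry must have recovered from the adverse events of that treatment, with limited exceptions (Section 4.1.2, exclusion 3). Patients irradiated on study carry acute radiation toxicity into the reporting window and are reviewed more closely while it lasts. A pooled rate combines radiation toxicity, any effect of the combination and some extra ascertainment, in proportions set by how many patients happened to choose concurrent radiation.

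The protocol itself treats the concurrent regimen as a distinct safety question. Section 4.2 calls for minimizing lung dose because of pneumonitis risk, Section 3.1.4 discusses that risk, and Section 4.6.1.3 refers to these patients as an arm, although Section 1.0 lists one treatment group. The six-patient safety run-in in Section 8.0 does not require any of the six to have concurrent radiation. As written, the plan therefore specifies no safety estimate for that regimen.

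**Working it through.** **Plan's own precision figure.** The only one concerns DFS: a 95% interval about 25% wide for 37 patients at 80% disease-free. The normal approximation gives 2 × 1.96 × √(0.8 × 0.2 / 37) = 25.8%, so it reproduces. No precision is stated for safety.

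**How long the review schedules differ.** Inputs: radiation as 44 twice-daily fractions over 22 days, or 33 once-daily fractions (Section 3.1.1); pembrolizumab starting 4 to 10 days after radiation begins (Section 4.2); up to 34 three-week cycles, or 102 weeks (flow chart footnote e). Five treatment days a week for the once-daily schedule is my assumption. Overlap = radiation duration − lag.
- Twice daily, 22 calendar days: (22 − 10)/7 = 1.7 weeks to (22 − 4)/7 = 2.6 weeks.
- Once daily, 33/5 × 7 = 46.2 days: (46.2 − 10)/7 = 5.2 weeks to (46.2 − 4)/7 = 6.0 weeks.
- If the 22 days are treatment days at five a week (30.8 calendar days): 3.0 to 3.8 weeks.

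Weekly review therefore covers about 1.7 to 6.0 weeks of pembrolizumab treatment, or 2% to 6% of 102 weeks. The extra reviews are overlap/1 week − overlap/3 weeks, about 1 to 4, against up to 34 cycle reviews. The overlap is a larger part of the first three cycles (9 weeks), the run-in's safety window: 1.7/9 = 19% to 6.0/9 = 67%.

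**What pooling does to a rate.** Pooled rate = f × p₁ + (1 − f) × p₀, where f is the concurrent share and p₁ and p₀ are the rates with and without concurrent radiation. The documents give none of these. With p₁ = 30% and p₀ = 15%, assumed for illustration:

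| f | Pooled rate | Below p₁ by | Above p₀ by |
|---|---|---|---|
| 10% | 16.5% | 13.5 points | 1.5 points |
| 25% | 18.75% | 11.25 points | 3.75 points |
| 50% | 22.5% | 7.5 points | 7.5 points |
| 75% | 26.25% | 3.75 points | 11.25 points |
| 90% | 28.5% | 1.5 points | 13.5 points |

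If p₁ = p₀, pooling distorts nothing.

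**What zero pneumonitis events would support.** The exact two-sided 95% upper limit for 0/n is 1 − 0.025^(1/n).
- All patients, n = 37: 9.5%.
- Concurrent group only: n = 28, 12.3%; n = 18, 18.5%; n = 9, 33.6%.

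Zero is a plausible result. At the 3.4% Grade 3/4 rate that Section 3.1.4 cites from the lung cancer trial, the chance of no event is 0.966^18 = 54% in 18 patients and 0.966^37 = 28% in 37.

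**Whether the groups could be compared.** For 30% against 15% (assumed), a two-sided 5% test of two proportions has power of about 19% with 18 and 19 patients, and about 20% with 9 and 28. The breakdown can describe the groups but not test between them.

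**The case against.** The strongest reply is that little turns on this. The Section 8.0 sentence is general and does not forbid a breakdown. Weekly review is brief, and both groups then follow the same schedule. All events through 30 days after treatment must be reported (Section 7.1), the diary is daily, and only Grade 2+ non-hematologic and Grade 3+ hematologic events are recorded (Section 10.1 item 5). The comparison group is not radiation-free either, since patients may have completed radiation before entry (Section 4.1.1, item 12), so a split does not isolate pembrolizumab plus endocrine toxicity. No decision rule, sample size or DFS analysis changes.

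Most of this stands, and it rules out some stronger readings that a reader might reach:
- That concurrent patients are questioned three times as often as the others. This is true only during the radiation period.
- That three-weekly review misses most short events. The diary and the reporting duty make this collection over the whole interval, and the documents give no basis for a figure.
- That a split would test the Section 3.1.4 statement "we would not expect significantly higher rates of pneumonitis as a result of the concurrent radiation". That is a background expectation about a choice made by preference, and the upper limits above are far too wide to check it.

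The reply does not supply the missing analysis. A breakdown that is merely not forbidden can be chosen, or left out, after the data are seen. Low power argues against a test, not against showing the groups.

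**Conclusion.** The point holds as a gap in specification. Safety is a listed primary objective and the treated population mixes two exposures by choice. The variable that separates them is collected, and the plan does not use it. The main reason to split is the radiation toxicity inside the window. The difference in ascertainment is real but short, about 1.7 to 6.0 weeks.

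The size depends on a concurrent share that the documents do not give and on whether rates differ. A reader might infer that the pooled table necessarily describes neither regimen; that does not follow. With few concurrent patients it nearly describes the non-concurrent regimen and hides the other, and with equal rates it is unbiased for both. A reader might also infer that pooling makes the concurrent evidence look about twice as precise. For the zero-event limit that is so only near a 50% share (18.5/9.5 = 1.9). The ratio is 12.3/9.5 = 1.3 with 28 concurrent patients and 33.6/9.5 = 3.5 with 9. The change is worth making before the safety data are analyzed, but it does not affect the DFS conclusions.

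**What to change.** Replace the Section 8.0 sentence with wording to this effect: adverse events will be tabulated by grade and category separately for patients with and without concurrent radiation, with the number of patients in each group and exact 95% intervals for pneumonitis and for any Grade 3+ event. In the concurrent group, events during the radiation period will be shown separately from later events. A table for all patients will also be given. The breakdown is descriptive, with no between-group test, and the non-concurrent group may have had earlier radiation.

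The tables need one denominator. Section 7.1 counts anyone with any dose as evaluable for safety, while Section 8.0 counts patients who completed three cycles. The two should be reconciled, because the radiation overlap falls inside those cycles.

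The cost is SAP wording, a few extra tables from data already collected, and wider intervals in each group than in the pooled table. No new patients, visits or data are needed.
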